7.4. Definitions of Evidence of Clinical Interest (ECI)

Selected non-serious and serious adverse events can also be classified as Events of Clinical Interest (ECI) and must be reported as described in section 7.6.

The following ECIs for this study must be reported to the Sponsor within 24hrs of learning of the event:

1. An overdose of pembrolizumab, as defined in Section 7.7 that is not associated with clinical symptoms or abnormal laboratory results.
2. A Drug induced liver injury (DILI) defined as elevated AST or ALT lab value that is greater than or equal to 3X the upper limit of normal

AND / OR

An elevated total bilirubin lab value that is greater than or equal to 2X the upper limit of normal **AND / OR**

An alkaline phosphatase lab value that is less than 2X the upper limit of normal, as determined by way of protocol-specified laboratory testing or unscheduled laboratory testing.

NOTE: These events will also be reported to MSD by the sponsor.

3. Any AEs identified in the below table can be classified as immune-related events of clinical interest. A detailed narrative of the event should be recorded as an ECI as described in section 7.6:

Pneumonitis - (deemed as an ECI if ≥ Grade 2 to be reported through the AE reporting pathway)		
Acute interstitial Pneumonitis	Interstitial Lung Disease	Pneumonitis
Colitis - (deemed as an ECI if ≥ Grade 2 or any grade resulting in dose modification or use of systemic steroids to treat the AE to be reported through the AE reporting pathway)		
Intestinal Obstruction	Colitis	Colitis microscopic
Enterocolitis	Enterocolitis hemorrhagic	Gastrointestinal perforation
Necrotising colitis	Diarrhoea	
Endocrine - (deemed as an ECI if ≥ Grade 3 or ≥ Grade 2 and resulting in dose modification or use of systemic steroids to treat the AE and will be reported through the AE reporting pathway)		
Adrenal Insufficiency	Hyperthyroidism	Hypophysitis
Hypopituitarism	Hypothyroidism	Thyroid disorder
Thyroiditis	Hyperglycemia, if ≥Grade 3 and associated with ketosis or metabolic acidosis (DKA)	
Endocrine (deemed as an ECI and will be reported through the AE reporting pathway)		
Type 1 diabetes mellitus (if new onset)		
Hematologic - (deemed as an ECI if ≥ Grade 3 or any grade resulting in dose modification or use of systemic steroids to treat the AE and will be reported through the AE reporting pathway)		
Autoimmune haemolytic anaemia	Aplastic anaemia	Thrombotic thrombocytopenic purpura
Idiopathic thrombocytopenia purpura	Disseminated intravascular coagulation	Haemolytic uraemic syndrome
Any grade 4 anaemia regardless of underlying mechanism		
Hepatic - (deemed as an ECI if ≥ Grade 2 or any grade resulting in dose modification or use of systemic steroids to treat the AE and will be reported through the AE reporting pathway)		
Hepatitis	Autoimmune hepatitis	Transaminase elevations (ALTand/or AST)
Infusion reactions - (deemed as an ECI for any grade to will be reported through the AE reporting pathway)		
Allergic reaction	Anaphylaxis	Cytokine release syndrome
Serum sickness	Infusion reactions	Infusion-like reactions
Neurologic - (deemed as an ECI for any grade and will be reported through the AE reporting pathway)		
Autoimmune neuropathy	Guillain-Barre syndrome	Demyelinating polyneuropathy
Myasthenic syndromw		
Ocular - (deemed as an ECI if ≥ Grade 2 or any grade resulting in dose modification or use of systemic steroids to treat the AE and will be reported through the AE reporting pathway)		
Uveitis	Iritis	
Renal - (reported as ECI for ≥ Grade 2 and will be reported through the AE reporting pathway)		
Nephritis	Nephritis autoimmune	Renal Failure
Renal failure acute	Creatinine elevations - (report as ECI if ≥ Grade 3 or any grade resulting in dose modification or use of systemic steroids to treat the AE)	
Skin - (deemed as an ECI for any grade and will be reported through the AE reporting pathway)		
Dermatitis exfoliate	Erythema multiforme	Stevens-Johnson Syndrome
Toxic epidermal necrolysis		
Skin - (deemed as an ECI for ≥ Grade 3 and will be reported through the AE reporting pathway)		
Pruritus	Rash	Rash generalised
Rash maculo-papular	Any rash clinical significant in the physicians judgement.	
Other - (deemed as an ECI for any grade and will be reported through the AE reporting pathway)		
Myocarditis	Pancreatitis	Percarditis
Any other grade 3 event which is considered immune-related by the physician.		

Table 9: Immune related AEs considered ECIs.

Patients should be assessed for possible ECIs prior to each dose. Lab results should be evaluated and patients should be asked for signs and symptoms suggestive of an immune-related event. Patients who develop an ECI thought to be immune-related should have additional testing to rule out other etiologic causes. If lab results or symptoms indicate a possible immune-related ECI, then additional testing should be performed to rule out other etiologic causes. If no other cause is found, then it is assumed to be immune-related.

7.5. Reporting of SAEs

Any SAE whether or not related to pembrolizumab, occurring from randomisation until 30 days following cessation of treatment, or the initiation of new anti-cancer therapy, whichever is earlier, must be reported on an SAE report form within 24 hours to the Sponsor of the PI or designee becoming aware of the event to the via [contact]** or email to [contact]. It will be the responsibility of the Sponsor to also inform MSD at the same time. All SAEs regardless of causality, pregnancy (as per section 7.2.2) or overdose (as per section 7.7) should be documented and each episode of an SAE must be recorded on a separate SAE report form. The NCI CTCAE Version 4 must be used to grade each SAE, and the worst grade recorded.

If new or amended information on a previously reported SAE becomes available, the Investigator should report this to the Sponsor using a new SAE report form. If the SAE has not been reported within the specified timeframes, a reason for lateness must be included when sending the SAE report form. Please refer to the SAE completion guidelines for further information.

Additionally, any SAE, considered by an investigator (who is a qualified physician) to be related to pembrolizumab that is brought to the attention of the investigator at any time outside of the time period specified in the previous paragraph also must be reported immediately to the Sponsor who will also inform MSD.

7.5.1. Events exempt from being reported as SAEs

Events specified in this section do not require reporting as SAEs in this trial, unless hospitalisation is prolonged for any reason and then an SAE form must be completed. The events must still be recorded in the appropriate section of the electronic case report form (eCRF).

1. Elective admissions to hospital for procedures which were planned and documented in the medical records at the time of consent are not SAEs, and do not require SAE reporting.
2. Hospitalisation for administration of the IMP, or to facilitate study procedures according to the trial protocol, is also exempt from being reported as an SAE.

7.5.2. Determining SAE Causality and Expectedness

Assessment of causality and expectedness for all SAEs will be made by the PI/designee and Chief Investigator or delegate against the current version of the Investigator Brochure section on Reference Safety Information. If updated versions of the Investigator Brochure are released during the course of the trial then assessment of expectedness will be made against the current regulatory approved version.

7.6. Reporting of ECIs

An ECI, irrespective of etiology or whether or not related to the Pembrolizumab, occurring from the first dose until 30 days following the last treatment dose, or the initiation of a new anticancer therapy, whichever is earlier; must be recorded on the AE eCRF. ECIs as described in Section 7.4 should be reported within 24 hours of the PI/designee becoming aware of the event to the sponsor. Please refer to the current Investigator Brochure for further information in the Reference Safety Information section. All other ECIs described in Table 10 will be reported as per adverse event reporting pathways.

7.7. Definition of an Overdose for This Protocol and Reporting of Overdose

At present no specific information is available on the treatment of overdose of pembrolizumab. For purposes of this trial, an overdose will be defined as any dose exceeding the prescribed dose for pembrolizumab by 20% over the prescribed dose. In the event of overdose the patient should be observed closely for signs of toxicity. Appropriate supportive treatment should be provided if clinically indicated.

If an adverse event(s) is associated with ("results from") the overdose of pembrolizumab, the adverse event(s) should be recorded on the AE eCRF and documented in the patients' medical records. The AE should also be reported as a serious adverse event, even if no other seriousness criteria are met. If an overdose is taken without any associated clinical symptoms or abnormal laboratory results, the overdose is again recorded as an AE on the eCRF and reported as a non-serious Event of Clinical Interest (ECI), using the terminology "accidental or intentional overdose without adverse effect."

All reports of overdose either SAE or ECI must be reported within 24 hours of the PI or designee becoming aware of the event to the Sponsor via [contact] who will also inform MSD.

7.8. Definition of a Serious Adverse Reaction (SAR)

A SAR is defined as a SAE that is judged to be related to any dose of study drug administered to the patient.

7.9. Definition of Suspected, Unexpected, Serious, Adverse Reactions (SUSARs)

A SUSAR is any SAR that is NOT consistent with the applicable product information as set out in the current Summary of Product Characteristics (SPC).

7.10. Reporting of SUSARs

The Investigator and local study team will rapidly report all SUSARs to the Sponsor within 24 hours of becoming aware of the event. The Sponsor will ensure that SUSARs are notified to the appropriate Regulatory Authority, the relevant Research Ethics Committee (REC)/Regulatory Authority (RA), MSD, the Sponsor and the participating Principal Investigators as appropriate in accordance with regulatory requirements and within the required timelines. Follow up of patients who have experienced a SUSAR should continue until recovery is complete or the condition has stabilised.

7.11. Annual Reporting of Serious Adverse Events

Annual reports will be submitted to the RA and REC by the Sponsor in accordance with all applicable global laws and regulations. Copies will be forwarded to the Sponsor and Investigators.

7.12. Urgent Safety Measures

The Sponsor or Investigator may take appropriate urgent safety measures (USMs) in order to protect the patient of a clinical trial against any immediate hazard to their health or safety. This includes procedures taken to protect patients from pandemics or infections that pose serious risk to human health. USMs may be taken without prior authorisation from the competent authority. The Medicines and Healthcare products Regulatory Agency (MHRA) and the Research Ethics Committee (REC) must be notified within three days of such measures being taken. Should the site initiate a USM, the Investigator must inform RM-CTU either by:

Email: [contact]

[contact]

[contact]

The notification must include:

- the date of the USM
- who took the decision; and
- why action was taken

RM-CTU will then inform the Sponsor who will notify the MHRA and the REC immediately and in writing within three days of USM initiation. RM-CTU will distribute the response and any subsequent amendments to the trial sites.

CI Contact Details:

Name: [name]

Address: Renal and Melanoma Unit

The Royal Marsden NHS Foundation Trust

[name]

[name]

[contact] [contact]

Email: [contact]

8.0. STATISTICAL ANALYSIS

8.1. Statistical Analysis Plan Summary

This is a multicentre, open label, randomised phase II study to assess the efficacy of pembrolizumab alone and in combination with high dose radiotherapy. Patients will be randomised into either arm of the study in a 1:1 ratio and stratified to take account of their baseline LDH and previous anti-CTLA4 treatment.

8.2. Sample Size and Power Considerations

The sample size of this study was calculated using a 2-sided α of 5%; power of 80%; RECIST response rate in the pembrolizumab arm is 30%; RECIST response rate in the pembrolizumab and radiotherapy arm is 50%. The study will randomise 234 patients in total (210 minimally required for statistical power calculation purposes, 105 patients in each arm; 20 additional patients to account for potential drop outs – an expected drop out rate of 10%) over 18 months i.e. 11-12 patients per month in approximately 15 to 24 UK centres. In the event that enrolment is slower than expected the Trial Steering Committee will consider adding additional UK sites. Patients enrolled in the trial are expected to be recruited from the routine clinics of the participating centres.

8.3. Randomisation

Patients will be randomised in a 1:1 ratio to receive pembrolizumab alone or pembrolizumab in combination with radiotherapy using random permuted blocks within strata to take account of their LDH level at baseline and previous anti-CTLA4 treatment.

Randomisation of enrolled patients will be stratified based on the following parameters;

1. LDH (below or within normal range / above upper limit of the normal range) and
2. Previous anti-CTLA4 treatment (yes/no)

The randomisation number is a unique number. Patients will be identified using the number generated by the database which will become their unique identifier throughout the study and in all future correspondence..

8.4. Data Analysis

The clinical data will be entered and stored in the PERM electronic database. Statistical analysis will be conducted using STATA software version 13.

8.4.1. Analysis populations

The efficacy results of the trial will be analysed on an intention to treat (ITT) basis. The ITT population is defined as all patients randomised in the study and are analysed as randomised for response rate, PFS and OS.

The safety data will be analysed by treatment received, irrespective of randomisation, in patients who received at least one treatment dose. Patients withdrawn prior to the first treatment dose will be excluded.

In addition, after 50% of the patients have been randomised and are evaluable for the primary endpoint an interim analysis will be carried out to assess the difference between the two trial arms. In the event that both arms showed a RECIST response rate of 30% when approximately 120 patients are evaluable then it will be judged unlikely that the pembrolizumab and radiotherapy arm will show a RECIST response rate of 50% relative to the 30% RECIST response rate in the pembrolizumab only arm at the end of the trial and the trial will be stopped.

Furthermore when 50% of the patients have been recruited this will be reviewed by the independent members of the TSC only, within a closed session. They will also decide if the results of the analysis needs to be released to the TMG, and whether any changes to the study should be implemented in terms of its continuance

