Best overall response is determined once the participant has discontinued the study medication. It is defined as the best response designation, as determined by the investigator, recorded between the date of randomisation and the date of objectively documented progression per RECIST v1.1 or the date of subsequent therapy, whichever occurs first. For participants without documented progression or subsequent therapy, all available response designations will contribute to the best overall response assessment. The participant's best overall response assignment will depend on the findings of both target and non-target disease and will also take into consideration the appearance of new lesions. The duration of objective response is measured from the time

measurement criteria are first met for CR or PR (whichever is first recorded) until the first date that PD is objectively documented.

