8.5. Planned method of analysis

Continuous data will be summarised using means, standard deviations, medians, minimum and maximum values and where appropriate 95% confidence intervals. Nominal and ordinal categorical data will be summarised using the number of observations and percentages. All significance tests will be two-sided using an overall alpha level of 5%. It is anticipated that adjustment will be made for repeated significance testing using a Bonferroni correction specifically for all secondary endpoints.

Primary Endpoint:

- The RR 12 weeks post treatment will be summarized as the percentage (including 95% confidence intervals) of responders and will be compared between treatment arms using the chi-squared test for proportions.

Secondary Endpoints:

- The RR at 6 months will be summarized as a percentage (including 95% confidence intervals) of responders and will be compared between treatment arms using the chi-squared test for proportions.

- To measure individual lesion response assessment every 12 weeks within each patient using McNemar's test of paired proportions between time points.
- The proportion of patients experiencing grade 3-5 toxicity will be compared on a regimen basis using the chi-squared test. Fishers exact test will be used when expected cell frequencies are <5.
- PFS and OS at 1, 2 and 3 years, respectively, will be calculated using Kaplan-Meier methods. Median PFS and OS with associated 95% confidence intervals will be presented by treatment and compared using the log rank test. Cox Proportional hazards regression model analysis will be used to calculate the hazard ratio between treatments along with its 95% confidence intervals and will be adjusted for other identified prognostic factors in a multivariate setting.

Exploratory Endpoints:

- Continuous exploratory data will be summarised using means, standard deviations, medians, minimum and maximum values attaching 95% confidence intervals where appropriate. Categorical data will be summarised using frequencies and proportions, attaching confidence intervals where necessary.

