8.7. Early Discontinuation of the Study

An interim analysis will be carried out when approximately 120 patients (50%) are evaluable for the primary endpoint, this will allow for the early termination of the trial should there be no difference between the two arms, respectively. No formal stopping rules are planned either for efficacy, futility or toxicity since this study is similar to routine standard of care with the addition of radiotherapy. The

Trial Steering Committee will monitor trial progress including for significant safety / toxicity issues should they arise.

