10.8.1. Trial Management Group

A Trial Management Group (TMG) will be set up and membership will include Chief Investigator, Chief Co Investigator, Trial Statistician and Trial Manager. Principal Investigators and other key study personnel will be invited to join the TMG as appropriate. The TMG have operational responsibility for the conduct of the trial.

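### Interim results by arm may be released to the TMG while the trial is still running, and the interim is not expressly limited to stopping for lack of difference

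*Combined protocol and SAP*

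**What the plan says.** Section 8.4.1 plans one interim comparison of the arms on the primary endpoint, at about 120 evaluable patients. Only the independent TSC members see it, in closed session. Section 10.8.2 likewise excludes the co-chief investigators when the TSC acts as the data monitoring committee.

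Of those independent members, section 8.4.1 then says: "They will also decide if the results of the analysis needs to be released to the TMG". It also leaves to them whether the study should change as regards its continuance. It gives no criterion for release and does not tie release to a stopped trial.

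Under section 10.8.1 the TMG consists of the chief investigator, the co-chief investigator, the trial statistician and the trial manager. In addition, "Principal Investigators and other key study personnel will be invited to join the TMG as appropriate".

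On stopping, section 8.4.1 says the trial stops if both arms show a 30% response rate. Section 8.7 also gives the purpose as ending the trial when the arms do not differ, but continues: "No formal stopping rules are planned either for efficacy, futility or toxicity". Section 8.5 sets an overall two-sided 5% level and foresees that "adjustment will be made for repeated significance testing using a Bonferroni correction specifically for all secondary endpoints". It makes no allowance for the interim look at the primary endpoint.

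The trial is open label (6.3.10). Section 5.3.8 does not require confirmation of response. For best overall response it says: "It is defined as the best response designation, as determined by the investigator".

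**The concern.** The closed session exists so that the people running the trial do not learn how the arms compare while patients are still being entered and assessed. The release clause lets that protection be lifted at discretion. If investigators knew the interim difference, it could affect which patients they put forward and how they read borderline scans, and a 12-week response in an open-label trial is exposed to both.

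The second issue is what the session may decide. The interim is described as a check for no difference, yet the authority over continuance has no stated direction, and nothing says that a favourable difference cannot end the trial. If it did so at a conventional level, with the final test also at 5%, the stated overall 5% would not hold.

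**Working it through.** **Inputs from the documents.** Section 8.2: response 30% against 50%, two-sided 5%, 80% power, 105 per arm (210), 234 randomised, 11-12 patients per month. The total of 234 over 18 months implies 13 per month. Sections 8.4.1 and 8.7: interim at about 120 evaluable. Section 8.5: chi-squared test.

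**Reproducing the plan's sample size.** Without continuity correction, n = [1.96·√(2·0.4·0.6) + 0.8416·√(0.3·0.7 + 0.5·0.5)]² / 0.2² = 93 per arm. With the correction, n = (93/4)·[1 + √(1 + 4/(93·0.2))]² = 102.8, so 103 per arm, within 3% of the stated 105. Then 210/0.9 = 233.3, rounded up to 234. The stated size is reproduced.

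**Patients exposed to a release.** 234 − 120 = 114, which is 49% of 234. Patients recruited in 12 weeks number 11·12/(52/12) = 30.5 to 13·12/(52/12) = 36. So about 31-36 patients would be awaiting their 12-week scan at the interim, and about 78-84 would not yet be randomised.

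**Effect of a shift after release (the shift sizes are assumptions).** True response is 30% in both arms, with 60 per arm at the interim and 57 more per arm by the final, 117 in all.
- A 5-point uplift in the 57 later radiotherapy-arm patients moves the final difference by 57·0.05/117 = 0.0244. The standard error is √(2·0.3·0.7/117) = 0.0599, so the test statistic moves by 0.0244/0.0599 = 0.407.
- Two-sided error = P(Z > 1.96 − 0.407) + P(Z < −1.96 − 0.407) = 0.060 + 0.009 = 6.9%.
- One million simulated trials give about 6.8%, against 5.0% with no shift.
- Opposite shifts of 3 points in the two arms give 7.8%, and of 5 points 12.9%. These are harsher, since they need upgrading in one arm and downgrading in the other.

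**Effect of the stopping decision, with no scoring shift.** The correlation between the interim and final statistics is √(120/234) = √0.513 = 0.716.

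| Use of the interim | Overall two-sided error with no true difference |
|---|---|
| No stopping | 5.0% |
| Stop only if observed difference ≤ 0 (illustrative), final at 5% | 2.5% |
| Stop for benefit at p<0.05, final at 5% | 8.5% simulated (8.3% by bivariate normal) |
| Stop for benefit at p<0.001, final at 5% | 5.0-5.1% |

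The benefit-stop rows count a significant interim in either direction. The 2.5% is below 5% because the futility stop removes nearly all the wrong-direction rejections. Under 30% against 50%, that same stop lowers power only from 88.7% to 88.4%.

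**The written trigger.** Read literally as 18/60 in each arm, the condition in section 8.4.1 occurs in about 1.2% of trials with no true difference at 30%. In practice the decision would rest on judgement.

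**The case against.** The strongest case against is that the plan does not intend what is feared. Both sections describing the interim give one purpose, stopping for lack of difference, and section 8.4.2 places the primary analysis after all patients have had their 12-week assessment. Release is reserved to independent members, so non-release is the starting position. The TSC charter, which is not among the documents, may restrict it further. Release once the trial has stopped would be unremarkable. This stands: the risk is permitted, not planned, and the 8.5% needs a rule that nobody has written.

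Three stronger readings are tempting, and the documents do not support them.
- *The plan as written inflates alpha.* It does not. A stop for no difference cannot raise the false-positive rate. Inflation needs an unwritten stop for benefit.
- *TMG members recruit patients and score the primary endpoint.* This is an inference. PIs join only as appropriate, and the investigator wording in section 5.3.8 defines best overall response, not the 12-week response. No section names the assessor of the 12-week response. Site investigators are the plausible reading. The central image review in section 6.1 is by the radiotherapy QA team and is not described as a blinded RECIST read.
- *The sample size may be changed on the interim result.* Section 8.6 mentions changes in final sample size only as an example of a protocol deviation whose handling the analysis plan will describe. It is not tied to the interim.

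It is also fair that the shift sizes have no source in the documents, and that open-label assessors already know the arm and the hypothesis. The figures do not isolate what release would add.

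**Conclusion.** The concern holds in a limited form. Section 8.4.1 protects the by-arm interim and then permits its release to the trial's leadership without limiting that to a stopped trial. Operational bias is the firmer harm. About 49% of patients would be enrolled or scored afterwards, on an unconfirmed response with no blinded read described. Its size cannot be derived from the documents; 6.8% against 5.0% illustrates one assumed shift.

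The alpha point is conditional. There is no inflation under the stated purpose, and about 8.5% if the trial were stopped for benefit at p<0.05 with the final test also at 5%. The plan should exclude that possibility in words. All the error rates assume a 30% response in both arms, 60 per arm at the interim and 117 per arm at the end.

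Separately, sections 8.4.1 and 8.7 contradict each other: one says the trial will stop under a stated condition, the other that no formal futility rule exists.

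**What to change.** 1. In section 8.4.1, replace the release clause with: *Only the recommendation to continue or stop is passed to the TMG; interim results by arm are not released unless the trial stops or the primary analysis is complete.* Carry the same wording into the TSC charter.
2. In sections 8.4.1 and 8.7, state that the interim can stop the trial for lack of difference only and cannot support an efficacy claim. The final test then stays at two-sided 5%. If an efficacy stop is wanted, specify Haybittle-Peto at two-sided p<0.001 with the final at 5% (overall error about 5.0-5.1%).
3. Reconcile sections 8.4.1 and 8.7 on whether a futility rule exists. If it does, state it as a range of results rather than the single outcome of 30% in both arms.

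The cost is a few sentences and no extra patients. The TMG gives up sight of the interim figures while the trial runs.
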